#### 4.2.2 Exclusion Criteria

Patients meeting one or more of the following criteria will not be eligible for the study:

- Severe pulmonary dysfunction at Screening (FVC < 40% predicted) or evidence of pulmonary exacerbation (note that pulmonary exacerbations refer to acute worsening respiratory symptoms resulting from a decline in lung function);
- Significant cognitive impairment in the judgement of the investigator who will be unable to follow the protocol;
- Patients with progressive neurological conditions (e.g., Parkinson's disease);
- Non-ambulant patients; or
- Pregnant women.

Template No.: RWI\_TP\_EPI0011 Revision 2 Reference: RWI\_WI\_EPI0005

ARMGO Pharma, Inc. RYR1-RM Study Version 4.0 dated 10-SEP -2024 Protocol/Study No.: CL-EPI-001 Page 24 of 64

## 4.2.3 Study Enrolment

The principal investigators (PIs) for the study will be neurologists who are routinely involved in the care and treatment of patients with *RYR1*-RM. Site selection criteria will include the projected availability of eligible patients in a 2.5-month enrolment period and the availability of the neurologist (and other site staff) to complete the assessments, case report forms (CRFs) and required study administration. Where possible, sites in each country specialised in treating RYR1-RM patients will be engaged in conducting the study. Selection criteria and basic site information (e.g., site size, investigator specialty, site type) will be collected via a site qualification survey.

Sites will assess initial eligibility for inclusion based on the patients' medical records (i.e., using information on their age, genetic diagnosis of *RYR1*-RM, and diagnosis of progressive neurological conditions). The eligibility criteria will be further assessed by a trained nurse/clinician during a telephone interview or as part of routine clinical care visits. For all eligible patients, the nurse/clinician will provide the Patient Information Sheet (PIS)/ICF to the patient for their review. If they agree to participate in the study, informed consent will be obtained from the patient (either independently or with the support of a caregiver, if required). Participants who consent to take part in the study will then be invited to attend the Screening Visit at the clinic (this may be conducted as part of their routine clinical care visits). At the Screening Visit, participants will be asked to confirm their consent to take part in the study (and sign the ICF if they have not done so already). Each site will maintain a Screening log to record the disposition of consecutive patients potentially eligible for study participation (e.g., demographic characteristics recorded in the patients' medical records), to better assess the representativeness of the sampled population.

#### 4.2.4 Participant Withdrawal

Participants may withdraw consent and stop participating in the study at any time, with no effect on their medical care or access to treatment. If a participant withdraws prior to completing the study follow-up period, any known reason for withdrawal should be documented in the database. All information already collected as part of the study will be kept for analysis; however, no other data will be collected from the patient as a part of the study beyond the reason for discontinuation. A decision to replace withdrawn patients will be made on an ongoing basis based on the impact of the study's ability to deliver against its objective.

## 4.3 Exposure Definition and Measures

This protocol does not recommend the use of any specific treatments. No study medication is provided as part of participation. No restrictions on concomitant treatments are associated with

Template No.: RWI\_TP\_EPI0011 Revision 2 Reference: RWI\_WI\_EPI0005

ARMGO Pharma, Inc. RYR1-RM Study Version 4.0 dated 10-SEP -2024 Protocol/Study No.: CL-EPI-001

Page 25 of 64

the study. All concomitant treatments will be carefully recorded to evaluate their potential influence on the outcomes of interest.

#### 4.4 Outcome Definition and Measures

#### 4.4.1 Endpoint Measures

#### 4.4.1.1 Primary Endpoint Measures

Absolute measurements at each study visit and changes in muscle strength measured by QMA, HHD, and MMT will be assessed between Screening, each visit as well as between consecutive visits. QMA will be used to assess knee flexion and extension, elbow flexion and extension, and shoulder abduction. Neck flexion will be measured using HHD and MMT (Error! Reference source not found.). Additional tests that will be performed to measure muscle strength include the 10-MWT, 1-Minute-Sit-to-Stand Test, and Stair Climb Test. The Screening measurement will be the baseline for the study. All tests should be conducted at the same time of day and in a standardized order for all participants across the study sites as follows:

- a) QMA;
- b) HHD;
- c) MMT;
- d) 10-MWT;
- e) 1-Minute-Sit-to-Stand Test; and lastly
- f) Stair Climb Test.

Table 2. Method of assessment for muscle strength measurements

Method of assessment	Muscle movement
	Knee Extension
	Knee Flexion
QMA a	Elbow Extension
	Elbow Flexion
	Shoulder Abduction
HHD	Neck Flexion
MMT	Neck Flexion

HHD, Hand-Held Dynamometry; MMT, Manual Muscle Testing; QMA, Quantitative Muscle Assessment.

Template No.: RWI\_TP\_EPI0011 Revision 2 Reference: RWI\_WI\_EPI0005

<sup>a For QMA, each muscle movement will be tested on both limbs (noting which is the dominant limb and starting with the dominant limb).

ARMGO Pharma, Inc. RYR1-RM Study Version 4.0 dated 10-SEP -2024 Protocol/Study No.: CL-EPI-001 Page 26 of 64

a) Quantitative Muscle Assessment (QMA)

QMA is a quantitative muscle testing (QMT) method that will be used to assess knee flexion and extension, elbow flexion and extension, and shoulder abduction. QMA is designed to measure Maximum Voluntary Isometric Contraction (MVIC), an objective and validated measure of muscle strength. MVIC has been adopted for the measurement of muscle strength in participants with neuromuscular disorders across several studies (18), and it has been shown to be a more reliable assessment tool than MMT methods. (19) MVIC can be measured using a strain gauge (which is attached to the participant on a standard plinth at one end and to orthopaedic bars at the other) or an HHD.

The QMA system consists of the following items (18, 20):

- QMA computer software package (Aeverl Medical, Gainesville, GA) (21), inclusive of a strain gauge, hand dynamometer, and data acquisition pad;
- OMT Frame;
- Standard double plinth; and
- Cuff and straps.

In this study, the QMA assessment of knee flexion and extension, elbow flexion and extension, and shoulder abduction will be conducted using a strain gauge. This method uses a fixed myometry assessment, namely a relative fixed point (i.e., frame) that the participant is instructed to exert maximum effort. (20) The testing procedure involves using an adjustable cuff to attach the participant's arm or leg to an inelastic strap that is connected to an adjustable frame with a load of 0.5 to 1,000 Newtons. The cuff is worn by the participant, and the participant is positioned on the plinth in such a way as to isolate the specific muscle movement under assessment. (22)

The QMA software package is a computer-based system that is designed to assist with the quantitative testing of muscle strength. This system converts the data generated through the test into a usable and comprehensible format and can generate reports about the results of the assessments. Detailed instructions for the use of the QMA software package can be found in the QMA user guide. (23, 24)

The QMA will be conducted at Screening, Visit 1, Visit 2, and End of Study Visit. Each muscle movement will be tested on both limbs (noting which is the dominant limb and starting with the dominant limb) and in a standardized order across sites. Three measurements per visit will be performed for each muscle movement, while the participant is verbally encouraged by the tester to exert maximal effort. For each trial, the maximum force that is generated by the

Template No.: RWI\_TP\_EPI0011 Revision 2 Reference: RWI\_WI\_EPI0005

ARMGO Pharma, Inc. RYR1-RM Study Version 4.0 dated 10-SEP -2024 Protocol/Study No.: CL-EPI-001

Page 27 of 64

participant will be recorded. The highest score of the three measurements can be used to determine the final strength level of the muscle movement tested. (22)

The raw QMA scores are measured in Newtons and can be converted into Pounds or Kilograms. The raw scores can also be standardised and expressed as deviation from normative values derived from healthy individuals. (25) The individual and average values of the three measurements taken for each muscle movement will be presented as both raw scores and deviations from normative data in the statistical analysis (see Section 6.2).

Further information on the QMA procedure and muscle movements assessed is provided Table 3. (18)

Table 3. QMA procedure and muscle movements assessed

Muscle movement	Position of	Strap position	Stabilisation by	Instruction
	participant		tester	
Knee Extension	Sitting, hips and	Proximal to ankle	Pressure through	Straighten your knee.
	knees at 90°	joint	shoulder and pelvis	Do not hold the couch
Knee Flexion	Sitting, hips and	Proximal to ankle	None	Bend your knee. Do
	knees at 90°	joint		not hold the couch
Elbow Extension	Supine, shoulder in	Proximal to wrist	Anterior surface of	Straighten your elbow
	neutral elbow in		shoulder and	
	90°flexion		lateral elbow	
Elbow Flexion	Supine, shoulder in	Proximal to wrist	Anterior surface of	Bend your elbow
	neutral elbow in		shoulder and volar	
	90° flexion		surface of elbow	
Shoulder	Supine, shoulder in	Proximal to elbow	Axilla and lateral	Bring your arm away
Abduction	90° abduction		trunk	from your body
				without
				lifting your arm off the
				bed

QMA, Quantitative Muscle Assessment.

Source: Meldrum et al. (18)

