Data will be extracted from the participants' medical records (both paper and/or electronic) at the Screening Visit (at site) and entered in an electronic case report form (eCRF). This data will be used to capture the participant's full medical history (starting from the earliest record available), including the date of *RYR1*-RM diagnosis, comorbidities, and medication use. Medical records may also be used to assess other clinical characteristics, including vital signs, forced vital capacity (FVC) and electrocardiogram (ECG) (if available in the participants' medical records within 12 months prior to the Screening Visit).

Data collected at study visits will be manually entered into the eCRF. The following data will be collected from participants at relevant time points for study assessments and procedures:

- Medical history (including biopsy details, if performed);
- Medication use (including all current and prior medications to treat symptoms of *RYR1*-RM);
- Full physical, neurological, and functional examination;
- Vital signs (heart rate, blood pressure, respiratory rate, temperature), FVC sitting and supine, and ECG;
- Strength measurements by QMA (shoulder abduction, elbow flexion and extension, knee flexion and extension), MMT (neck flexion), and HHD (neck flexion);
- 10 Meter Walk Test;
- 1-Minute Sit-to-Stand:
- Stair Climb Test; and
- PROMIS Fatigue, PROMIS-PF, IPAQ, and symptom diary.

Participants will be given periods of rest in between tests to reduce their burden. Ideally, all visits should be conducted in the morning to minimise the impact of the participant's daily activities on their energy levels, cognitive function, and mood. However, the actual timing of the visits may vary according to the capacity of the sites.

For details on data collected at each visit refer to the data collection schedule table in Section 4.5.

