# 4.5.1 Screening Visit

The following data will be collected at the Screening Visit for all enrolled participants (listed in the order in which they will be collected during the visit):

- Informed consent;
- Inclusion/Exclusion (including MMT to assess muscle/motor function deficit, 10-MWT to assess ability to walk, and FVC to assess pulmonary dysfunction);
- Demographics (medical records);
- Medical history (medical records);
- Medication use (medical records);
- Vital signs and ECG (medical records or primary data collection; note that FVC will be evaluated as part of the assessment of the exclusion criteria);
- Strength measurements using QMA and HHD (note that MMT will be conducted at the start of the Screening Visit as part of the assessment of the inclusion criteria);
- 1-Minute Sit-to-Stand Test;
- 4SCT:
- Full physical, neurological, and functional examination;
- PROMIS Questionnaires;
- IPAO:
- Syde® device fitting;
- Symptom diary (initiation); and
- AE/SAE.

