#### 5. DEVICES

The use of digital tools, such as wearable devices and other remote sensors, allows for the continuous, objective, and sensitive measurements of a participant's functional ability during daily life. Validated class I medical wearable devices have been used in clinical trials for assessing functional outcomes in daily life for participants with neuromuscular disorders (48) including clinical trials of participants with Duchenne Muscular Dystrophy and can be used in both ambulant and non-ambulant participants with movement disorders. (49)

Participants will be provided with a wearable device to collect daily physical activities. The purpose of the wearable device is to accurately measure the movement and activity levels of

Template No.: RWI\_TP\_EPI0011 Revision 2 Reference: RWI\_WI\_EPI0005

ARMGO Pharma, Inc. RYR1-RM Study Version 4.0 dated 10-SEP -2024 Protocol/Study No.: CL-EPI-001

Page 42 of 64

the participant during normal daily living, outside of investigational site visits. The Syde® device consists of 2 sensors (and a docking station). It is a Class I medical device manufactured by Sysnav. There are no foreseeable risks and minimal inconveniences to the participants who will wear it. Participants will wear one sensor on each ankle.

As the wearable device battery requires recharging daily after use, the sensors will not be worn at night. Site personnel, the participant, and parents/caregivers will be trained on the correct use of the device. The device will be fitted on the participant in the clinic prior to the Stair Climb Test, in order to ensure that it is working well, which can be assessed as participant climbs the stairs. The device would be removed when participants take part in activities which could damage the sensors or where the device could be in contact with water. Detailed user instructions are provided in the wearable device participant manual and quick start guide.

The wearable device will be worn on both ankles daily for 30 ( $\pm$ 3) days (to be taken off only at night before sleeping) from Screening Visit [Syde® device fitting] to Visit 1 [Syde® device removal]).

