The quantity of data recording will be closely monitored by Sysnav and communicated to the sites to maintain an adequate participant compliance throughout the recording period, until the end of the study. The recorded data will then be checked for accuracy, completeness, relevance, and consistency, before the last step of data analysis which includes the process of using algorithms to generate the Syde® clinical variables.

The wearable device will not be worn during clinic visits, but participants will resume use immediately following completion of in-clinic tests. Subjects must return the wearable device in the event of screen failure, early termination, or after study completion.

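### The protocol gives two test orders for Screening, the study baseline; under one of them four of the six primary tests change position between Screening and follow-up

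*Protocol*

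**What the plan says.** Section 4.4.1.1 states "The Screening measurement will be the baseline for the study" and then asks for all tests to be done "in a standardized order for all participants across the study sites as follows": QMA, HHD, MMT, 10-MWT, 1-Minute Sit-to-Stand, Stair Climb. It makes no exception for Screening.

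Section 4.5.1 describes its Screening list as "listed in the order in which they will be collected during the visit". The second item is "Inclusion/Exclusion (including MMT to assess muscle/motor function deficit, 10-MWT to assess ability to walk, and FVC to assess pulmonary dysfunction". QMA and HHD come several items later, with the remark "note that MMT will be conducted at the start of the Screening Visit as part of the assessment of the inclusion criteria". Sit-to-Stand and 4SCT follow. Neither MMT nor 10-MWT appears again in the list. The synopsis gives the same Screening sequence.

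Section 4.5.2 lists QMA, HHD, MMT, 10-MWT, Sit-to-Stand and 4SCT for Visit 1, Visit 2 and End of Study. It does not itself call this an order, but it agrees with 4.4.1.1.

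On the ankle sensors, Section 5 says "The device will be fitted on the participant in the clinic prior to the Stair Climb Test", so that they can be checked on the stairs. It also says "The wearable device will not be worn during clinic visits". Section 4.5.1 lists the fitting after the 4SCT.

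**The concern.** Section 2 says the study is meant to find how many measurements give a stable baseline. It also expects QMA scores to rise with practice without any gain in strength. The first change, Screening to Visit 1, is where that practice effect should show most. If the tests run in one order at Screening and another afterwards, that change contains both learning and the effect of a different amount of preceding work, and nothing in the design separates them.

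A systematic shift does not average out over participants. Nor would the correlation coefficients planned in Section 6.2.2.1 reveal it, because adding a constant to every Visit 1 value leaves a correlation unchanged. The disease background names fatigue as a symptom, so an effect of preceding effort is plausible. If some sites follow 4.4.1.1 and others 4.5.1, the baseline order would also differ between sites.

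**Working it through.** The protocol gives no figure to reproduce: it has no sample size calculation, no SD and no order-effect size. The check is therefore a comparison of positions and preceding work, followed by an illustration.

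**Positions.** Screening from 4.5.1, follow-up from 4.4.1.1 and 4.5.2.

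| Test | Screening | Follow-up | Shift | Same tests before it? |
|---|---|---|---|---|
| QMA | 3 | 1 | 2 earlier | no |
| HHD | 4 | 2 | 2 earlier | no |
| MMT | 1 | 3 | 2 later | no |
| 10-MWT | 2 | 4 | 2 later | no |
| Sit-to-Stand | 5 | 5 | 0 | yes |
| 4SCT | 6 | 6 | 0 | yes |

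**Preceding work.** Inputs from 4.4.1.1:
- QMA: 5 movements × 2 limbs × 3 trials = 30 maximal efforts (reading the three trials as per limb)
- HHD: 3 efforts
- MMT: 3 neck-flexion efforts
- 10-MWT: 2 comfortable + 2 fast = 4 walks

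This assumes that the eligibility MMT and 10-MWT are the endpoint measurements.

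| Test | Before it at Screening | Before it at follow-up |
|---|---|---|
| QMA | 3 MMT efforts + 4 walks | none |
| HHD | 3 MMT efforts + 4 walks + 30 QMA | 30 QMA |
| MMT | none | 30 QMA + 3 HHD = 33 |
| 10-MWT | 3 MMT efforts | 30 + 3 + 3 = 36 |

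For 10-MWT the difference is 36 − 3 = 33 efforts. Of these, 2 knee movements × 2 limbs × 3 = 12 are knee efforts, 3 arm movements × 2 × 3 = 18 are arm efforts, and 3 are neck efforts.

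**Direction.** If earlier tests tire participants, QMA and HHD are measured less fresh at Screening than later. Their change from Screening is then pushed upward, the same way as learning. MMT and 10-MWT are measured fresher at Screening, so their change is pushed downward, against learning.

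**Changes affected.** Section 6.2.1 summarises changes from Screening to each follow-up visit and between consecutive follow-up visits. The former carry the shift for the four tests. Visit 1 to Visit 2 and Visit 2 to End of Study compare visits run in the same order and do not.

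**Illustration only.** With n = 20 (Section 6.1), the 95% confidence interval for a mean change has half-width t(0.975, 19)/√20 = 2.093/4.472 = 0.47 SD of the change. If an order effect biases the mean change by d SDs, coverage of the true change is P(|T| < 2.093), where T is noncentral t with 19 degrees of freedom and noncentrality d√20.

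| Assumed d | Coverage |
|---|---|
| 0.1 | 93% |
| 0.2 | 86% |
| 0.3 | 75% |
| 0.5 | 44% |

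The values of d are assumptions. With one order at all four visits, every shift in the first table is 0; learning would remain in the change from Screening.

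**The case against.** Several points on the other side stand.

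- A reader might infer that every change from Screening is affected. It is not: Sit-to-Stand and 4SCT keep their place and the same preceding tests.
- A reader might infer that the shift always mimics learning. For MMT and 10-MWT it would work against it.
- A reader might attach a definite bias to the 33 extra efforts before 10-MWT. The documents give neither the cost of prior effort nor a within-participant SD, and only 12 of those efforts load the knees.
- For QMA, which matters most, the extra listed work at Screening is small: four short walks and three neck-flexion efforts, and QMA does not test the neck. If the eligibility MMT covers more muscles, the work is larger; the protocol does not settle this.
- Section 4.1 provides rest between tests. No duration is given, so how much it helps is unknown.
- The bias need not be equal across participants. Fatigability varies, and a site that follows 4.4.1.1 at Screening has no shift.
- Table 9 has separate rows for eligibility and 10-MWT, so separate measurements might be intended. Section 4.5.1 points the other way for MMT, since it explains that test's absence from the strength step by the eligibility assessment.

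The time-of-day wording does not support the point. Section 4.4.1.1 asks for the same time of day, while Section 4.1 prefers mornings but allows that "the actual timing of the visits may vary according to the capacity of the sites". That is a mild tension with no clear direction of bias.

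None of this removes the contradiction between 4.4.1.1 and 4.5.1.

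**Conclusion.** The contradiction is real and should be fixed. If 4.5.1 is followed, four of the six primary tests move two places between baseline and follow-up. For those four, an order effect cannot be told apart from learning in the change from Screening. This matters most for QMA, where both would act in the same direction and where the protocol expects learning.

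The size is unknown. The coverage figures show only what an assumed bias would do with 20 participants. The study is descriptive, stability can still be judged from Visit 1 onward, and rest may reduce the effect. A stronger claim, that the study's baseline results are known to be biased by a stated amount, is not supported.

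The sensor wording is a secondary inconsistency. If the sensors are fitted before the Screening 4SCT and not worn at later visits, the test conditions differ; no effect of the sensors on 4SCT is shown.

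**What to change.** Reconcile Sections 4.4.1.1, 4.5.1 and 4.5.2 and the synopsis so that the scored tests run in one identical order at all four visits. There are two ways:

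1. Put MMT and 10-MWT first at every visit. This fits the eligibility step and removes the shift. The price is that QMA no longer comes first at any visit.
2. State that the eligibility MMT and 10-MWT are separate from the baseline measurements, and take the latter in the 4.4.1.1 order. The price is a few repeated efforts at Screening, and the eligibility efforts still precede QMA there.

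In either case, say which muscles the eligibility MMT covers.

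For Screening visits already done in the 4.5.1 order, flag the difference in the report and read the stability of QMA, HHD, MMT and 10-MWT mainly from Visit 1 onward.

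Also reconcile Section 4.5.1 with the two statements in Section 5, so that the scored 4SCT is done under the same sensor condition at every visit.

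The cost is protocol wording and a memo to sites. The first option adds no tests; the second adds one short repeat of MMT and 10-MWT at Screening.
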